#### 5.5.1 Study Drug Discontinuation

Treatment with Nivolumab will be discontinued if treatment cannot be tolerated (toxicity), due to disease progression, or for whom treatment could not be resumed after non-toxicity related hold (see Section 5.5).

Those subjects who discontinue from treatment regardless of reason will be followed as described in section 6.1. Time and Events Schedule.

See Section 7.2 for handling of participants who withdraw from the study.

### 5.6 Expected Toxicities for Nivolumab

Expected toxicities for monotherapy Nivolumab are listed below.

Common side effects of nivolumab are: (≥ 10%)

- Fatigue
- Rash
- Diarrhea

- Nausea
- Itching, burning, numbness or weakness, possibly in arms, legs, hands, and feet
- Thyroid gland function change
- Joint pain or stiffness

Side effects of Nivolumab are: ( $\geq 1\%$ )

- Increased Alkaline phosphate, ALT (alanine aminotransferase) an/or AST (aspartate aminotransferase)
- Amylase increased
- Creatinine increased
- Decreased appetite
- Dry Mouth
- Inflammation of the colon and mouth
- Dry skin
- Loss of color (pigment) from areas of skin
- Swelling, including face, arms, and legs
- Fever
- Headache
- Infusion related reaction
- Lung inflammation (pneumonitis – see additional information below)

Uncommon side effects of Nivolumab are: ( $\geq 0.1\%$ )

- Change in hormones
- Allergic reaction
- Bronchitis
- Respiratory failure
- Disturbance of nerves
- Vertigo (a sensation of feeling off balance; dizziness)
- Heart rate increased
- Hypertension (increased blood pressure)
- Hives
- Dry eye
- Hair loss
- Inflammation of the eye, heart, kidney, pancreas, pituitary gland, stomach, thyroid gland, liver
- Renal failure
- Blurred vision
- Hepatitis
- Inflammation of the heart

Rare side effects of Nivolumab are: ( $\geq 0.01\%$ )

- Lipase increased (lab test result associated with pancreas inflammation)
- Abdominal pain
- Increased liver function test

- Decreased appetite
- Encephalitis
- Pericardial effusion
- Pericarditis
- Enteritis
- Constipation
- Asthenia
- Immune-mediated hepatitis
- hypertransaminasaemia
- Anaphylactic reaction (severe allergic reaction)
- Damage to the protective covering of the nerves in the brain and spinal cord
- Diabetes complications resulting in excess blood acids
- Skin inflammatory reaction, including severe reaction
- Guillian-Barre syndrome – an autoimmune disorder associated with progressive muscle weakness or paralysis
- Inflammation of blood vessels, brain, potentially life-threatening
- Myasthenic syndrome (neurologic syndrome characterized by muscle weakness) including myasthenia gravis, a nerve disease that may cause weakness of eye, face, breathing, and swallowing muscles
- Polymyalgia rheumatic
- Rhabdomyolysis – muscle fiber released into the blood stream
- Rosacea
- Sarcoidosis – a disease involving abnormal collections of inflammatory cells (granulomas) in organs such as lungs, skin, and lymph nodes
- Histiocytic necrotizing lymphadenitis or Kikuchi lymphadenitis – disorder of the lymph nodes which causes the lymph nodes to become enlarged, inflamed and painful, commonly affecting lymph nodes of the neck and possibly associated with fever or muscle and joint pains.

**Lung Inflammation (Pneumonitis):** It is possible that nivolumab may cause inflammation of the tissues of the lung. This adverse effect has been reported infrequently in patients treated with nivolumab. While many patients with X-ray or CT abnormalities have not developed any symptoms, some patients have developed mild to severe symptoms and in rare cases, death has occurred as a result of their lung inflammation. Signs and symptoms of lung inflammation may include difficulty breathing, pain or discomfort while breathing, chest pain, cough, shortness of breath, increase rate of breathing, fever, low blood oxygen levels, or fatigue.

### **5.7. Procedures for Subjects Exhibiting Immune-Related Adverse Events**

Immune-related AEs may be defined as an AE of unknown etiology, associated with drug exposure and consistent with an immune phenomenon. Immune-related AEs may be predicted based on the nature of the nivolumab compound, its mechanism of action, and reported experience with immunotherapies that have a similar mechanism of action. Special attention must be paid to AEs that may be suggestive of potential irAEs. An irAE can occur shortly after the first dose or several months after the last dose of treatment.

[figure not shown]
Recommendations for management of specific immune-mediated AEs such as pneumonitis, enterocolitis, hepatitis, dermatitis, neuropathies, endocrinopathies, and other immune-mediated AEs are detailed in the sections below.

### 5.7.1. Procedures and Guidelines for Pneumonitis

Subjects with symptomatic pneumonitis must immediately stop receiving nivolumab and have an evaluation. The evaluation may include bronchoscopy and pulmonary function tests to rule out other causes such as infection. If the subject is determined to have study drug–associated pneumonitis, the suggested treatment plan is below.

## Pulmonary Adverse Event Management Algorithm

Rule out non-inflammatory causes. If non-inflammatory cause, treat accordingly and continue I-O therapy. Evaluate with imaging and pulmonary consultation.

Patients on IV steroids may be switched to an equivalent dose of oral corticosteroids (e.g. prednisone) at start of tapering or earlier, once sustained clinical improvement is observed. Lower bioavailability of oral corticosteroids should be taken into account when switching to the equivalent dose of oral corticosteroids.

### 5.7.2. Procedures and Guidelines for Enterocolitis

[figure not shown]
Subjects must be carefully monitored for signs and symptoms of enterocolitis (such as diarrhea, abdominal pain, mucus or blood in stool, with or without fever) and of bowel perforation (such as peritoneal signs and ileus). In symptomatic subjects, infectious etiologies should be ruled out and endoscopic evaluation must be considered for persistent or severe symptoms. Recommendations for

management of enterocolitis are shown below.

## GI Adverse Event Management Algorithm

Rule out non-inflammatory causes. If non-inflammatory cause is identified, treat accordingly and continue I-O therapy. Opiates/narcotics may mask symptoms of perforation. Infliximab should not be used in cases of perforation or sepsis.

[figure not shown]
Patients on IV steroids may be switched to an equivalent dose of oral corticosteroids (e.g. prednisone) at start of tapering or earlier, once sustained clinical improvement is observed. Lower bioavailability of oral corticosteroids should be taken into account when switching to the equivalent dose of oral corticosteroids.

### 5.7.3. Procedures and Guidelines for Hepatitis

Liver function tests (hepatic transaminase and bilirubin levels) must be monitored and signs and symptoms of hepatotoxicity must be assessed before each dose of nivolumab. In subjects with hepatotoxicity, infectious or malignant causes must be ruled out and frequency of LFT monitoring increased until resolution. Recommendations for management of hepatitis are shown below.

## Hepatic Adverse Event Management Algorithm

Rule out non-inflammatory causes. If non-inflammatory cause, treat accordingly and continue I-O therapy. Consider imaging for obstruction.

Patients on IV steroids may be switched to an equivalent dose of oral corticosteroids (e.g. prednisone) at start of tapering or earlier, once sustained clinical improvement is observed. Lower bioavailability of oral corticosteroids should be taken into account when switching to the equivalent dose of oral corticosteroids.

\*I-O therapy may be delayed rather than discontinued if AST/ALT ≤ 8 x ULN or T.bili ≤ 5 x ULN.

[figure not shown]
\*\*The recommended starting dose for grade 4 hepatitis is 2 mg/kg/day methylprednisolone IV.

### 5.7.4. Procedures for Immune-Mediated Dermatitis

Monitor subjects for signs and symptoms of dermatitis such as rash and pruritus. Unless an alternate etiology has been identified, signs or symptoms of dermatitis must be considered immune mediated. Recommendations for management of dermatitis are shown below.

## Skin Adverse Event Management Algorithm

Rule out non-inflammatory causes. If non-inflammatory cause, treat accordingly and continue I-O therapy.

Patients on IV steroids may be switched to an equivalent dose of oral corticosteroids (e.g. prednisone) at start of tapering or earlier, once sustained clinical improvement is observed. Lower bioavailability of oral corticosteroids should be taken into account when switching to the equivalent dose of oral corticosteroids.

\*Refer to NCI CTCAE v4 for term-specific grading criteria.

[figure not shown]
^If SJS/TEN is suspected, withhold I-O therapy and refer patient for specialized care for assessment and treatment. If SJS or TEN is diagnosed, permanently discontinue I-O therapy.

### 5.7.5. Procedures for Immune-Mediated Neuropathies

Subjects must be monitored for symptoms of motor or sensory neuropathy such as unilateral or bilateral weakness, sensory alterations, or parenthesis. Recommendations for management of neuropathies are shown in table below.

# Neurological Adverse Event Management Algorithm

Rule out non-inflammatory causes. If non-inflammatory cause, treat accordingly and continue I-O therapy.

Patients on IV steroids may be switched to an equivalent dose of oral corticosteroids (e.g. prednisone) at start of tapering or earlier, once sustained clinical improvement is observed. Lower bioavailability of oral corticosteroids should be taken into account when switching to the equivalent dose of oral corticosteroids.

[figure not shown]
## 5.7.6. Procedures for Immune-Mediated Endocrinopathies

Subjects must be monitored for clinical signs and symptoms of hypophysitis, adrenal insufficiency (including adrenal crisis), and hyper- or hypothyroidism. Subjects may present with fatigue, headache, mental status changes, abdominal pain, unusual bowel habits, and hypotension or with nonspecific symptoms which may resemble other causes such as brain metastasis or underlying disease. Unless an alternate etiology has been identified, signs or symptoms of endocrinopathies must be considered immune-mediated.

Thyroid function tests and clinical chemistries must be monitored at the start of treatment, before each dose, and as clinically indicated based on symptoms. In a limited number of subjects, hypophysitis was diagnosed by imaging studies through enlargement of the pituitary gland. Recommendations for management of endocrinopathies are shown below.

## Endocrinopathy Management Algorithm

[figure not shown]
Rule out non-inflammatory causes. If non-inflammatory cause, treat accordingly and continue I-O therapy. Consider visual field testing, endocrinology consultation, and imaging.

Patients on IV steroids may be switched to an equivalent dose of oral corticosteroids (e.g. prednisone) at start of tapering or earlier, once sustained clinical improvement is observed. Lower bioavailability of oral corticosteroids should be taken into account when switching to the equivalent dose of oral corticosteroids.

### 5.7.7. Procedures for Immune-Mediated Nephritis

Renal function tests (creatinine) must be monitored and signs and symptoms of nephrotoxicity must be assessed before each dose of nivolumab. In subjects with nephrotoxicity, infectious or malignant causes must be ruled out and frequency of Creatinine monitoring increased until resolution. Recommendations for management of nephritis are shown below.

### 5.7.8. Procedures for Other Immune-Mediated Adverse Reactions, Including Ocular Manifestations

Nivolumab must be permanently discontinued for severe immune-mediated adverse reactions. Systemic corticosteroids treatment should be initiated at a dose of 1 to 2 mg/kg per day of prednisone or equivalent for severe immune-mediated adverse reactions.

Corticosteroid eye drops must be administered to subjects who develop uveitis, iritis, or episcleritis. Nivolumab must be permanently discontinued for immune-mediated ocular disease that is unresponsive to local immunosuppressive therapy.

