### **5.5 Dose Modification and Dosing Delays**

Dose modification of nivolumab is not permitted in this study. In some circumstances, it may be

necessary to temporarily interrupt study treatments as a result of AEs that may have an unclear relationship to the study drug.

Treatment must be withheld for drug-related Grade 4 hematologic toxicities, non-hematological toxicity  $\geq$  Grade 3 (including laboratory abnormalities) or selected  $\geq$  grade 2 immune-related toxicities, and severe or life-threatening AEs. Treatment can be held for up to 8 weeks from date of last treatment. If steroids are needed, participant should be treated but if treatment must be withheld for greater than 8 weeks, participant must be permanently discontinued from study treatment.

Table 2 summarizes the dose administration guidance for nivolumab that must be implemented with the indicated related AEs. Additional information related to dose changes for nivolumab for specific AEs can be found subsequently.

Participants may resume treatment with study drug when the drug-related AE(s) resolve to Grade  $\leq 1$  or baseline value, with the following exceptions:

- Participants may resume treatment in the presence of Grade 2 fatigue
- Participants who have not experienced a Grade 3 drug-related skin AE may resume treatment in the presence of Grade 2 skin toxicity
- For participants with Grade 2 AST, ALT and/or Total Bilirubin Abnormalities, dosing may resume when laboratory values return to baseline and management with corticosteroids, if needed, is complete.
- Participants with combined Grade 2 AST/ALT OR total bilirubin values meeting discontinuation parameters must have treatment permanently discontinued.
- Drug-related pulmonary toxicity, diarrhea or colitis must have resolved to baseline before treatment is resumed. Participants with persistent Grade 1 pneumonitis after completion of a steroid taper over at least 1 month may be eligible for retreatment if discussed with and approved by the Lead Study PI.

Participants with drug-related endocrinopathies adequately controlled with only physiologic hormone replacement may resume treatment after consultation with the Lead Study PI. Adrenal insufficiency requires discontinuation regardless of control with hormone replacement.

**Table 2:** Dose Modification Guidelines for Drug-Related Adverse Events

Toxicity	Grade	Hold Treatment (Y/N)	Timing of Treatment Restart	Nivolumab	Discontinue Subject

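### A site working from Section 5.5 and Table 2 could restart nivolumab after a severe immune-mediated reaction for which Section 5.7.8 requires a permanent stop

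*Combined protocol and SAP*

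**What the plan says.** Section 5.7.8 covers the remaining immune-mediated reactions after the organ-specific subsections 5.7.1 to 5.7.7. Its rule is mandatory and mentions no restart: "Nivolumab must be permanently discontinued for severe immune-mediated adverse reactions". Eye disease has a separate criterion in the same section: "Nivolumab must be permanently discontinued for immune-mediated ocular disease that is unresponsive to local immunosuppressive therapy".

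Section 5.5 sets the general dosing rule. It says "Participants may resume treatment with study drug when the drug-related AE(s) resolve to Grade" 1 or lower, or to the baseline value, and then lists exceptions. These concern fatigue, skin, liver tests, lung and bowel toxicity, and endocrine events. Some are stricter than the general rule: "Drug-related pulmonary toxicity, diarrhea or colitis must have resolved to baseline before treatment is resumed", and "Adrenal insufficiency requires discontinuation regardless of control with hormone replacement".

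Section 5.5 also gives Table 2 binding force: "Table 2 summarizes the dose administration guidance for nivolumab that must be implemented with the indicated related AEs". In the Grade 3 non-hematologic row, treatment is held, then restarted at an unchanged dose once the toxicity resolves. Permanent discontinuation is mandatory there if the toxicity has not resolved within 6 weeks of the last infusion; for a severe or life-threatening event it has only to be considered. A note in the non-hematologic cell refers the reader to Section 5.5 for immune-related events. Section 5.5 also says: "Additional information related to dose changes for nivolumab for specific AEs can be found subsequently".

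**The concern.** Sites are likely to dose from a table they are told to implement. For this class of reaction the table, and the section its note points to, both leave re-treatment open, while the mandatory stop sits in 5.7.8, which neither names. Section 5.6 lists inflammation of the heart and of the pancreas among the effects of nivolumab. Neither has its own subsection in 5.7.1 to 5.7.7, so both fall under 5.7.8.

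At stake is full-dose re-exposure after a severe reaction, and different handling of the same event across the five named centers. The setting is adjuvant: on the retrospective rates in Section 1.2.1 (recurrence of about 32% in stage IIB and 46% in stage IIC), more than half of such patients did not recur. This is a matter of patient safety and consistent dosing, not of the statistical design.

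**Working it through.** No figure in the plan needs to be reproduced; the check is a comparison of texts. Take a first reaction of the 5.7.8 type, not ocular, recorded as Grade 3 and judged severe, that falls to Grade 1 within 6 weeks of the last infusion.

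| Source | Instruction for this patient |
|---|---|
| 5.7.8 | Stop permanently |
| 5.5, resume rule | May resume; no listed exception applies |
| Table 2, Grade 3 row | Restart at the same dose; a permanent stop is to be considered |
| Table 2 note on immune-related events | Go to 5.5, which returns the reader to the resume rule |

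1. **Do the 5.5 exceptions catch the case?** No. Each names an organ system or symptom outside 5.7.8. Where the authors wanted a mandatory stop in 5.5 they wrote one, for adrenal insufficiency.
2. **Does the note lead to 5.7.8?** No. It points to the section in which Table 2 itself sits. The immune-related procedures are in 5.7, whose introduction says that other immune-mediated events are dealt with below it.
3. **Is precedence stated?** Not in readable text. The sentence in 5.5 about further information on specific events names no section and does not say which rule governs.
4. **Does the problem extend to Grade 4?** No. Table 2 also bars restart for Grade 4 non-hematologic toxicity, in agreement with 5.7.8.
5. **What does severe mean?** Section 8.4.3 labels Grade 3 as severe, but that is a scale for recording adverse events. The withholding rule in 5.5 lists Grade 3 or higher non-hematologic toxicity and then, as a further item, severe or life-threatening events. Table 2 uses the word in its Grade 2 and Grade 4 rows as well. The dosing text does not treat it as a synonym for Grade 3.

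The doses in dispute for one such patient can be bounded. Section 3.4 plans 12 doses, one every 4 weeks, and the text under Table 2 says skipped doses are not made up. After dose k, the doses left are 12 − k if the event resolves before the next is due, or 11 − k (minimum 0) if one is skipped. The second case fits the hold limit: "Treatment can be held for up to 8 weeks from date of last treatment".

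- k = 1: 11 or 10 doses
- k = 6: 6 or 5 doses
- k = 11: 1 or 0 doses
- k = 12: 0 doses

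Section 5.7.8 allows 0 throughout. This range bounds one patient's exposure. It does not measure how often the problem would arise.

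**The case against.** The strongest reply is that nothing collides. Section 5.5 permits resumption and 5.7.8 forbids it for a named class; a site that stops treatment breaks no rule, and a specific mandatory rule would ordinarily be taken to govern a general permission. Table 2 is described as a summary, 5.5 announces further text on specific events, and the Grade 3 row already asks for a permanent stop to be considered. All of this stands, so a reader who infers that the protocol gives two instructions that cannot both be followed goes too far. What is left is the site that stops reading at 5.5 and Table 2, and nothing readable there directs it to 5.7.8.

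Three other inferences are tempting and unsupported:

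- **That severe in 5.7.8 is settled as Grade 3.** The usage in 5.5 and Table 2 points the other way. If the word means clinical judgment, the mandatory stop rests on an undefined term, which also needs repair.
- **That the note under Table 2, requiring a stop when the same severe event recurs, shows that restart after a first 5.7.8 reaction was intended.** The note serves the whole table, including hematologic events with an explicit restart, so it shows nothing about this class.
- **That every severe eye reaction is caught.** Ocular disease has its own criterion in 5.7.8, and the text does not say whether the general sentence also applies.

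Finally, the management figures are not available, including one in the introduction to 5.7. A precedence rule in one of them cannot be excluded.

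**Conclusion.** The point holds as an operational inconsistency with a misdirected cross-reference. A site working from 5.5 and Table 2 could re-challenge a patient for whom 5.7.8 requires permanent discontinuation; a site that reads all three can comply with all three. It is worth correcting because it bears on patient safety and the correction is cheap.

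The number of patients affected cannot be derived. Section 5.6 places inflammation of the heart and pancreas among uncommon effects but gives no frequency by severity. The primary endpoint, sample size and alpha are not affected.

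The conclusion assumes that the missing figures contain no precedence rule and that some reactions judged severe under 5.7.8 would be graded at a level where Table 2 allows restart. Confidence is medium for those reasons.

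**What to change.** 1. Change the Table 2 note so that it refers to Sections 5.5 and 5.7 for immune-related events.
2. Add to the 5.5 exceptions and to the Table 2 Grade 3 non-hematologic row: *For severe immune-mediated reactions covered by 5.7.8, stop nivolumab permanently and do not restart; 5.7.8 prevails over Table 2 for these events.*
3. Have the sponsor state the grade meant by severe in 5.7.8 and whether laboratory-only events count. The new line should not fix Grade 3 before that is confirmed. If the definition can reach Grade 2, the same line belongs in that row, which also allows restart.
4. Keep the separate criterion for ocular disease unless the sponsor decides otherwise, and leave the other organ-specific rules in 5.5 in force.

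The cost is a short wording amendment with IRB approval, and no added visits, tests or patients. The downside is that some patients whose severe reaction of this kind has resolved lose the option of re-treatment. How many depends on the definition chosen in step 3, which is why laboratory-only events should be addressed explicitly.

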## **5.8. Dietary Restrictions**

### Patients on a controlled sodium diet

Each mL of this medicinal product contains 0.1 mmol (or 2.5 mg) sodium. To be taken into consideration when treating patients on a controlled sodium diet.

## **6. STUDY SCHEDULE**

### **6.1. Time and Events Schedule**

**Table 3.** Time and Events Schedule is on the following page.

	Screening	Treatment Cycle (4 Week Cycle) a												Follow up (months) k										End of Treatment (EOT)/Withdrawal m
														M1 Post-Scans	Every 3 months from last Infusion x 1 year				Every 6 months subsequently x2 years				Final Year	
															M3	M6	M9	M12	M18	M24	M30	M36	M42 and M48	
	28 Days*	1	2	3	4	5	6	7	8	9	10	11	12		M3	M6	M9	M12	M18	M24	M30	M36	M42 and M48	
Informed Consent	X																							
History and Physical Exam b	X	X	X	X	X	X	X	X	X	X	X	X	X	x	X	X	X	X	X	X	X	X	X	X
Vital Signs	X	X	X	X	X	X	X	X	X	X	X	X	X	X	X	X	X	X	X	X	X	X	X	X
Beta HCG Pregnancy Test c	X	X	X	X	X	X	X	X	X	X	X	X	X											
ECOG Performance Status	X	X	X	X	X	X	X	X	X	X	X	X	X	X	X	X	X	X	X	X	X	X	X	X
Laboratory Assessments d	X	X	X	X	X	X	X	X	X	X	X	X	X	X	X	X	X	X	X	X	X	X	X	X
Cross-sectional imaging, including at minimum chest, abdomen and pelvis e	X							X						X		X		X	X	X	X	X	X	X l
AE Assessment		Assessed at every visit																						
Research blood sample collection f	X j	X j			X			X			X			X		X		X	X	X				X
CTC Analysis g	X j	X j			X									X										
Quality of Life Assessment (Appendix #1)		X	X	X	X	X	X	X	X	X	X	X	X			X		X	X	X	X	X	X	X
Nivolumab Therapy		X	X	X	X	X	X	X	X	X	X	X	X											
Archived tissue request	X																							

\*Screening period is a total of 28 days; Screening labs that are performed within 7 days prior to C1D1 do not need to be repeated

a. Treatment may be administered with a window of ± 7 days.

b. Visits may be performed with a window of ± 14 days. Long-term follow up may be discontinued once the primary end point is assessed and met.

c. If female of childbearing potential, a pregnancy test will be required at screening visit and prior to the start of each cycle of study drug.

d. Laboratory Assessments:

- Hematology labs to include hemoglobin, hematocrit, red blood cell count, white blood cell count, platelets (direct platelet count), as well as total and differential CBC counts. The CBC differential includes enumeration of neutrophils, lymphocytes, eosinophils, monocytes, basophils and any abnormal blood cells noted in the differential.
  - Chemistry laboratory analysis includes albumin, urea or BUN, creatinine, ALT, AST, LDH, serum alkaline phosphatase, total bilirubin, TSH, glucose, total protein, sodium, potassium, chloride, and CO2.
  - Hematology, chemistry and endocrine laboratory analysis to be performed within 7 days prior to each Nivolumab treatment
- e. CT or PET/CT imaging will be performed after the 6th infusion (prior to treatment cycle 7) and after the 12th infusion (prior to month 1 Follow-up). All scans during the 24 month follow-up period should be performed 6 months after last previous scan and at the discretion of the treating physician. After 24 months of follow-up, scans will be performed per standard of care or the discretion of the treating physician. If a participant discontinues treatment for any reason, including disease progression, scans and visits will resume at the next scheduled timepoint as indicated in the table.
- f. Research blood samples are optional for subjects. Samples will be drawn any time within the 28 day screening period up until pre-dose C1D1, every 3 months during nivolumab therapy, and then every 6 months thereafter through Month 24 of follow up.
- g. CTC analysis samples are optional for subjects. Samples will be drawn any time within the 28 day screening period up until pre-dose C1D1, at 3 months, and 12 months.
- h. Patients will be monitored for local or regional recurrence based on physical examination at their treatment visits and cross-sectional imaging.
- i. Screening labs and physical performed as part of screening can be used to satisfy Cycle 1 Day 1 requirements if completed within 7 days of first treatment
- j. Research Study samples and CTC Analysis can be collected any time during the screening period up until pre-dose Treatment Cycle 1.
- k. For the follow up visits occurring after the M1 visit can occur  $\pm 6$  weeks
- l. Per standard of care, performed if clinically indicated. Or if scans were done within 8 weeks, reports and images will be obtained.
- m. For patients who discontinue treatment due to disease progression, they will be followed only for survival every 3 months starting from the EOT visit. If information is available on subsequent treatments, this will be collected.

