### **2.2. Primary Endpoint**

- The primary end point is recurrence-free survival at 24 months. Recurrence-free survival time is defined as the number of days from study registration until documented progression or death without documentation of disease progression.

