### **3.4. Dose and Duration of Therapy**

Patients will receive nivolumab 480 mg as a flat dose IV over at least 30 minutes every 4 weeks for a total of 12 doses over the course of 48 weeks.

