#### **9.1.2. Survival and Recurrence-free Survival**

Patients' survival times will be measured from the initial date of treatment to the recorded date of death. Recurrence-free survival (RFS) will be measured from the initial date of treatment to the date of documented recurrence. Distant Metastases-free survival (DMFS) is defined as the time from definitive surgery to the date of diagnosis of metastatic disease.

Overall survival and recurrence-free survival (RFS) will be estimated by the Kaplan-Meier method. The corresponding median survival times (with 90% confidence limits) will be determined, as will the cumulative percentage of patients remaining progression-free / alive at selected time points after initial treatment (e.g., 6, 12, and 18 months).

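### For patients who complete 12 doses, no scheduled scan falls at the 24-month primary landmark, so recurrences found only by the next scan count as recurrence-free at 24 months

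*Combined protocol and SAP*

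**What the plan says.** Section 2.2: "The primary end point is recurrence-free survival at 24 months". That section starts the clock at registration, as the "number of days from study registration until documented progression or death". Section 9.1.2 starts it at first dose: "Recurrence-free survival (RFS) will be measured from the initial date of treatment to the date of documented recurrence". Both date a recurrence when it is documented.

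Section 3.4 gives nivolumab "every 4 weeks for a total of 12 doses over the course of 48 weeks". Section 5.5 says that held doses are skipped and not made up.

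Table 3 in Section 6.1 sets follow-up visits "Every 3 months from last Infusion x 1 year", then every 6 months, with imaging marked at M6, M12, M18 and M24 of follow-up. Footnote e places a scan after infusion 12 and continues: "All scans during the 24 month follow-up period should be performed 6 months after last previous scan". It also allows scans at the treating physician's discretion.

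Two footnotes give windows. Footnote b says "Visits may be performed with a window of ± 14 days". Footnote k begins "For the follow up visits occurring after the M1 visit can occur" and allows 6 weeks either way.

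Section 7.1 repeats the 6-month scan rule but counts visits in study months: every 3 months to study month 24, then every 6 months to study month 60.

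**The concern.** The endpoint clock starts at registration or first dose, while the follow-up clock in Table 3 starts at the last infusion. Twelve four-week cycles are about 11 calendar months, so follow-up M12 is not study month 24.

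A recurrence that becomes detectable between the scan at 22–23 months and month 24, and that is picked up only at the next scheduled scan, is dated at 28–29 months. The Kaplan-Meier estimate at 24 months then lies between the true 24-month rate and the rate at the last scan before it. In a single-arm trial tested against a fixed 70%, no control arm on the same schedule cancels this. The plan gives no rule for assessment at the landmark, for dating a recurrence found at a later scan, or for censoring a patient last assessed before month 24.

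**Working it through.** **The plan's own figure.** Section 9.3 gives 63 evaluable patients for 0.70 vs 0.85, one-sided alpha 0.05, power 0.90. For a one-sample test of a survival probability on the log(-log) scale, with g(S) = −ln(−ln S) and V(S) = (1−S)/(S·(ln S)²):

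n = [(1.645·√V(0.70) + 1.282·√V(0.85)) / (g(0.85) − g(0.70))]² = 64.9, so 65.

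Power at n = 63 is 0.894. The planned size is reproduced to within 2 patients, and this point does not change it.

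**Timing from first dose** (1 month = 30.44 days; all 12 doses on schedule).
- Dose 12 is at week 11 × 4 = 44, or 308/30.44 = 10.1 months. Cycle 12 ends at week 48, or 336/30.44 = 11.0 months.
- Counted from the last infusion: M12 = 10.1 + 12 = 22.1 months; M18 = 28.1 months.
- Scans chained from a post-infusion-12 scan at week 48: 11.0 + 12 = 23.0 months, then 29.0 months.
- With the ±6-week window (1.4 months), M12 spans 20.7–23.5 months (week-44 anchor) or 21.7–24.4 months (week-48 anchor). M18 comes no earlier than 26.7 months.
- From registration, assuming a gap of 0–28 days (the screening period), up to 0.9 month is added, so nominal M12 lies at 22.1–24.0 months.
- For early stoppers the timing varies if follow-up runs from their actual last infusion: with 7 doses M18 falls at 23.5 months, with 8 doses at 24.4.

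**Effect on the 24-month estimate.** Assume a constant hazard, so S(t) = S(24)^(t/24), and a benchmark without lag. If every event in the gap waits for the next scan, the estimate at 24 months equals S at the last scan. If half surface clinically, it lies halfway between that and S(24). This treats every gap event as a recurrence; deaths are dated when they occur.

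- Last scan 22.1 months: 0.70^(22.1/24) = 0.720.
- Last scan 23.0 months: 0.70^(23.0/24) = 0.7105.
- Last scan 20.7 months (M12 six weeks early): 0.70^(20.7/24) = 0.735.

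**Effect on type I error.** Section 9.3 names a non-parametric one-sample survival test but no cut-off. I assume an exact binomial rule at n = 63. The smallest count with P(X ≥ r | 0.70) ≤ 0.05 is r = 51, with alpha 0.035 and power 0.858.

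| Case (true RFS 70%) | RFS as read | P(X ≥ 51 of 63) |
|---|---|---|
| No lag | 70.0% | 3.5% |
| 23.0 months, half surface clinically | 70.5% | 4.3% |
| 22.1 months, half surface clinically | 71.0% | 5.1% |
| 23.0 months, all wait | 71.1% | 5.1% |
| 22.1 months, all wait | 72.0% | 7.1% |

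In patients, the on-schedule shift is at most 63 × 0.0105 = 0.7 to 63 × 0.020 = 1.3. A true 85% reads 85.6–86.1%. A normal-approximation test that spends the full 5% under the null would move to about 7–9% in the two all-wait cases.

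**The case against.** A reader might infer that no assessment of any kind falls at month 24. The documents do not support that. Section 7.1 describes a clinic visit at study month 24, and the window, a registration origin or early discontinuation can each put an assessment at or near the landmark. What stands is narrower: no scheduled scan falls there for patients who complete treatment, and Section 7.1 does not fit Table 3.

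A reader might also infer that gap recurrences would usually wait until month 28. The documents point the other way in part. Scans are also at the physician's discretion, physical examination is part of surveillance (footnote h), and one of the two retrospective studies cited for the recurrence rates has a title saying that symptoms are the most frequent indicator of recurrence. Recurrences found between scans are dated when found. The all-wait figures are therefore an upper bound for on-schedule visits.

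Nor is a net bias in favour of the drug established. Section 1.2.1 calls the 70% a conservative estimate from retrospective data and does not say how those recurrences were detected or dated. If they too were dated at documentation, part of the lag is shared.

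Finally, dating at documentation is a legitimate, explicit choice. That is a reason to keep it for the primary analysis, but not a reason to leave the schedule unaligned with the landmark or the effect unexamined.

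**Conclusion.** The point holds in limited form. For completers, scheduled imaging falls at about 22–23 and 28–29 months from first dose and misses the 24-month landmark, and the sections that define origin, anchor and window do not agree. The effect on the estimate is small: at most about 1–2 points at a true 70% on schedule, up to 3.5 points if M12 is done six weeks early, and about 0.5–1 point if half the gap recurrences surface clinically. Against a 15-point target this matters only for a borderline result, where type I error could move from 3.5% to 4.3–7.1% under the assumed cut-off. These figures rest on a constant hazard, completion of all 12 doses, first dose as the origin, and a benchmark without similar lag.

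**What to change.** 1. Reconcile Sections 2.2, 6.1 (Table 3 and footnotes b, e and k), 7.1 and 9.1.2 to one time origin, one follow-up anchor and one visit window. Define the already-planned outcome assessment nearest the landmark relative to 24 months from that origin, with no added scan.
2. Keep the Kaplan-Meier estimate with documented dates as the primary analysis.
3. Pre-specify a sensitivity analysis that estimates S(24) with recurrence interval-censored between the last negative and first positive assessment.
4. Do not automatically count a recurrence first found after month 24 as an event by month 24. Some will have arisen after the landmark, and the rule would reverse the bias.

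Cost: wording in Section 9 and the Table 3 footnotes, and a little more analysis work. One planned assessment may shift by about 1–2 months (24 − 23.0 to 24 − 22.1). The preceding follow-up scan is at about 16–17 months, so the 6-month rule in footnote e and Section 7.1 would have to be worded to agree; the trial team must settle that. The sensitivity estimate may be slightly less favourable, and it will not be fully comparable with a benchmark whose dating method is not stated. If the data are cut at 48 months as in Section 9.4, the last-enrolled patients will not yet have their 28–29 month scan, and they inform that analysis only up to their last negative assessment. The sample size does not change.
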